General aim and endpoint: To assess study feasibility and provide estimated effect sizes (point estimates with confidence intervals) for all measures of interest in order to plan an adequately powered study. We will assess recruitment rates and acceptability of treatment in arms involving exclusive enteral nutrition.

Primary outcome and endpoint: To assess the efficacy of 6 weeks of ECS in inducing remission (CDAI <150) compared to treatment with CS in adult patients with active CD (CDAI >220 and either CRP >5 or fecal calprotectin >250 mg/l).

Secondary outcomes and endpoints: To determine the beneficial effect of 6 weeks of ECS as compared to CS in inducing:

1. Clinical disease improvement (drop in CDAI >70 or 100)
2. Improvement in quality of life (using the Inflammatory Bowel Disease Questionnaire (increase IBDQ scores))
3. Biochemical remission (normalization of either serum CRP and/or fecal calprotectin)
4. Changes in microbiota composition (16S sequencing Illumina)
5. Normalization of colonic transit (SHAPE 0-5 markers at day 5)³⁴ among those with altered transit at baseline
6. Decrease in anxiety and/or depression scores (decrease >2 points HAD-A and/or HAD-D scores)
7. Increase in body weight and improvement in nutritional status (increased levels of micronutrients)
8. Decrease of indirect markers of mucosal integrity (IFABP2)
9. Changes in bacterial fermentation profile (SCFAs: acetate (acetic acid), propionate (propionic acid), and butyrate (butyric acid))^{26,27}.
10. Decreased number of adverse events

METHODS

Study design

Protocol date: October 2018

Randomized control trial; 3 arms of treatment: EEN plus standard or short course of CS (ECS, ECSC) vs CS alone (CS) conducted at McMaster University Medical Centre (Figure 1). The study will last 10 weeks and will involve 4 visits. At the screening visit, we will assess clinical history and symptoms, perform a physical exam and complete bloodwork after the informed consent is signed. Randomization will occur at the second visit (pre-treatment), when the inclusion and exclusion criteria and symptoms will be re-assessed, and baseline stool and urine samples will be collected. In addition, we will perform a SHAPE study and patients will be assessed by a dietitian or clinical nutrition support specialist to assess dietary factors and estimate energy needs using the Harris Benedict equation as detailed below.

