2. Confirmed CD diagnosis for at least 6 months
3. Clinically active disease (CDAI >220 or HBI>6) or evidence of activity in endoscopy
4. Biochemical evidence of disease activity (CRP > 5 and/or fecal calprotectin > 250),

Exclusion criteria:

1. Current treatment with EEN
2. Intestinal obstruction, perforation, toxic megacolon, massive gastrointestinal bleeding, abdominal abscess, or other criteria considered by the investigator which preclude the use of EEN;
3. Stricture disease
4. Previous intestinal resection with a remnant bowel <180 cm
5. Treatment with prednisone in last 30 days;
6. New start or change in dose of azathioprine, 6-mercaptopurine, cyclosporine, other immunosuppressant or biologics in the last 90 days. Doses of these medications must also remain unchanged for the duration of the study.
7. New start or change in dose of 5ASA in last 30 days. 5ASA dose must remain unchanged for the duration of the study.
8. Treatment with antibiotics or probiotics use in the last 30 days.
9. Pregnancy or lactation
10. Any serious illness considered by the investigator that will interfere with the study procedure or results.

Intervention

Participants will be randomized to one of the following interventions:

1. Exclusive enteral nutrition plus corticosteroids

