Patients randomized to ECS or ECSC arms will receive EEN defined as enteral feeds given exclusively as sole nutritional source over 6 weeks period in addition to the CS therapy. Hypercaloric polymeric formula (Modulen 1.5 kcal /ml; Nestle ^{22,23}) will be used for a period of 6 weeks. To increase palatability, patients will be allowed to add the “Nestle Nutrition Flavour Mix” (see Appendix). Daily volumes of formula will be prescribed based upon the patient’s estimated energy requirement (EER), calculated using the Harris Benedict equation (calculator available at <https://manytools.org/handy/bmr-calculator>), which estimates basal metabolic rate from weight and height and then applies an activity factor which ranges from 1.2 to 2.4 (Sedentary AF 1.2; mild activity 1.375, moderate activity AF 1.55, heavy activity AF 1.7, extreme AF 1.9 For details, refer to Appendix). Actual body weight or ideal body weight for height will be used in the equation depending on whether the patient is of an appropriate weight or underweight for height. Oral administration will be encouraged wherever possible, with formula volume distributed as set meals and snacks throughout the day. Nasogastric (NG) tube insertion for delivery of formula will be discussed and offered only if oral supplementation is not possible or not tolerated by the patient. Enteral feeding will be prescribed as an exclusive therapy, with exclusion of all normal diet for the period of feeding. Patients will be reviewed after 3 weeks of therapy and, when required, energy intakes will be modified by adjusting formula volumes based upon adequacy of weight changes. Volume taken per meal and distribution during the day will be recorded in the case report form. No oral foods or fluids

(except for clear liquids including water and weak tea or coffee) will be allowed during the study period. Vitamins and supplements will be allowed if doses have been stable before entering in the study, and doses are not changed during the study.

2. Corticosteroids

Patients in ECS and CS arms will receive oral prednisone 40 mg x day for 2 weeks; with subsequent taper of daily dose by 5 mg per week. Patients randomized to ECSC arm will receive oral prednisone 40 mg x day for 3 days and taper in 16 days (Figure 1). Patients randomized to the CS arm will be asked to maintain their regular diet.

Follow up after treatment

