Following the completion of the period of exclusive enteral feeding, patients receiving EEN will be instructed to gradually reintroduce foods by adding one individual item every 2 days as shown in Table 1 ^{32,33} and Appendix with instructions for food introduction with coincident reduction of formula volumes under the supervision of an expert in Nutrition. The accelerated introduction of foods was based on a recent study showing similar results with additional benefits of 2 days vs 4 days ³³.

Treatment compliance

The subjects will be asked to keep the cans of Modulen and blister packs of prednisone during the entire treatment period and bring them back to the investigator at the end of that period. Compliance will be recorded in the CRF. In order to improve assessment of patient's compliance, 2 copies of a paper sheet diary will be provided at Visit 1. Patients

consuming <80% of the prescribed treatment dose throughout the study, or those who interrupted therapy for more than three consecutive days will be considered as noncompliant.

Measurements before and after treatment

- Clinical data regarding demographics, disease location and activity (Harvey-Bradshaw Index), social life and habits, past and current clinical medical background, previous surgeries, nutritional status (malnourishment, weight/ height) will be collected in CRF.
- Dietitian/ Certified nutrition support clinician: Dietary habits and caloric intake will be recorded at baseline with nutritional assessment during visits
- Bloodwork to assess for inflammatory markers, CRP, fecal calprotectin, ESR, as well as CBC, platelets, micronutrients (albumin, vitamin D, B12, A, zinc, copper, chromium)
- Questionnaires: McMaster Food frequency questionnaire(Hamilton, ON), quality of life (SIBDQOL¹³), disease activity (CDAI), anxiety and depression (HAD score, Beck inventory), and nutritional assessment (Subjective Global Assessment¹⁴ Braun Nutriscreen program)
- Gastrointestinal transit (colonic transit: SHAPE study and orocecal transit^{24,25}: patient will take one capsule and have an x ray on day five, following R.C. Evans, et al protocol, where ≥ 6 markers indicate delayed transit, therefore ≤ 5 is normalization of colonic transit).³⁴
- Stool sample (frozen samples) for microbiota composition (16S sequencing Illumina; Dr. [name]'s lab) metabolomics and metagenomics ([name]?)¹⁵

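### The stable-dose condition for vitamins and supplements stands only in the EEN intervention text, although blood micronutrient levels are compared between ECS and CS

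*Combined protocol and SAP*

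**What the plan says.** Intervention item 1 (Exclusive enteral nutrition plus corticosteroids) opens by naming the arms it covers: "Patients randomized to ECS or ECSC arms will receive EEN defined as enteral feeds given exclusively as sole nutritional source". Its closing lines forbid ordinary food and most fluids during feeding, and its last sentence is the supplement condition: "Vitamins and supplements will be allowed if doses have been stable before entering in the study, and doses are not changed during the study". The sentence appears nowhere else.

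Intervention item 2 (Corticosteroids) gives the comparator one dietary instruction: "Patients randomized to the CS arm will be asked to maintain their regular diet". It does not mention supplements.

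The secondary outcomes are introduced with "To determine the beneficial effect of 6 weeks of ECS as compared to CS in inducing", and item 7 of that list is "Increase in body weight and improvement in nutritional status (increased levels of micronutrients". Under Measurements before and after treatment, the blood panel lists "micronutrients (albumin, vitamin D, B12, A, zinc, copper, chromium".

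The protocol does fix other doses for every arm. Exclusion criterion 7 adds "5ASA dose must remain unchanged for the duration of the study", and criterion 6 does the same for immunosuppressants and biologics. Neither mentions vitamins or minerals.

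**The concern.** A supplement acts directly on several of the analytes that outcome 7 measures. If one arm is held to stable supplement doses and its comparator is not, the ECS–CS difference mixes the effect of EEN with the effect of unequal supplement use. Treatment is not blinded, and patients see a dietitian or nutrition specialist at the second visit, so a low level could plausibly prompt a change after allocation is known. If the change is a new supplement in the CS arm, CS levels rise and the EEN effect looks smaller than it is.

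This matters even in a pilot without a powered test. The General aim is to produce effect sizes with confidence intervals for all measures of interest in order to plan the full trial, and a biased contrast would be carried into that planning.

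**Working it through.** **Side-by-side reading**

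- Does any all-arm rule cover supplements? Exclusion criteria 6 and 7 fix immunosuppressants, biologics and 5ASA. Criteria 5 and 8 bar recent prednisone, antibiotics and probiotics. None covers vitamins or minerals.
- Does the general clause on unauthorised treatments cover them? Early withdrawals treats such use as non-compliance and keeps the patient in the ITT analysis, but the document never lists what is unauthorised.
- Would the per-protocol set remove them? Statistical analysis defines that set by non-compliance with EN only, so a CS patient who starts a supplement stays in.
- Would the analysis adjust for them? Continuous outcomes get a t test or Mann–Whitney test with no supplement covariate.
- Would the data show them? Dietary habits and intake are recorded at baseline, with nutritional assessment at visits. No CRF item for starting or changing a supplement is described.

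The gap is therefore not closed elsewhere.

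**The plan's own figure**

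Three arms of 30 make 90, and 90 / (1 − 0.10) = 100, the stated recruitment total. The 30 per arm comes from a pilot rule with no alpha, power, effect size or SD. This point does not challenge it.

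**Illustration of the mechanism**

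All inputs except n = 30 are assumptions. Let d be the true EEN effect in SD, f the fraction of CS patients who start a supplement of the analyte, and s the rise it causes in SD.

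1. Observed difference = d − f·s. With f = 0.3 and s = 1 the shift is 0.3 SD, so d = 0.5 appears as 0.2.
2. Range: f·s runs from 0.2 × 0.5 = 0.1 to 0.5 × 1.0 = 0.5, so d = 0.5 appears as 0.4 down to 0.
3. Precision at 30 per arm: the 95% half-width is 1.96 × √(2/30) = 0.51 SD.
4. Power (two-sided 5% assumed, normal approximation) = Φ(difference/SE − 1.96). Without new supplements SE = √(2/30) = 0.258. With them the CS variance is 1 + f(1 − f)s², so for f = 0.3 and s = 1 it is 1.21 and SE = √(2.21/30) = 0.271.

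| True d | Power, f = 0 | Observed difference, f = 0.3, s = 1 | Power, f = 0.3, s = 1 |
|---|---|---|---|
| 0.75 | 83% | 0.45 | 38% |
| 0.50 | 49% | 0.20 | 11% |

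5. The expected sign changes only if f > d/s: above 50% for d = 0.5 and s = 1, above 75% for d = 0.75 and s = 1, and above 33% for d = 0.5 and s = 1.5.

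**Would leaving out the patients who started supplements be a valid check?**

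Suppose the CS patients in the lowest 30% at baseline are the ones who start. For a normal variable, the mean of the remaining 70% is φ(−0.524)/0.7 = 0.348/0.7 = 0.50 SD. With an assumed baseline to week-6 correlation of 0.7, the CS week-6 mean rises by 0.7 × 0.50 = 0.35 SD (0.25 to 0.45 for correlations 0.5 to 0.9). That lowers the ECS–CS difference again, by about as much as the 0.3 SD bias it was meant to check.

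**The case against.** The strongest reply is that the sentence names no arm. It speaks of entering the study and of doses during the study, in the manner of the all-arm stability rules, so it may be a general rule that landed in the wrong paragraph. That is plausible. A reader might infer that the sponsor deliberately set different supplement rules by arm, and the documents do not support that inference. What stands is that the text as placed binds only the EEN arms, and a site following it would have no rule for CS patients. Either reading calls for the same edit.

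Second, a reader might infer that supplements could reverse the nutritional result. The illustrated range for a true 0.5 SD effect is 0 to 0.4 SD and never goes negative. Reversal needs high uptake or a large supplement effect, and nothing in the documents points to either. Masking is the realistic risk.

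Third, the size is wholly assumed. The documents do not say that micronutrient results are returned or acted on. Screening bloodwork precedes randomisation, so any response before allocation would be common to the arms. Uptake also has to be counted analyte by analyte: starting vitamin D does not contaminate zinc, and albumin is not a vitamin or mineral supplement target. All of this stands, and it limits the claim to a possible bias of unknown size.

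Fourth, the confidence interval half-width of 0.51 SD exceeds the illustrated bias. That is true, but the interval describes random error and does not correct a systematic shift.

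**Conclusion.** The point holds in a limited form. The supplement condition is written in the EEN text alone, no equivalent exists for the CS arm, and an outcome compared between ECS and CS depends on that exposure. The likely direction is understatement of the EEN effect, on the assumption that CS patients start supplements more often than they stop them. The 0.3 SD figure is an illustration and not an estimate.

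The reach is the supplemented analytes within one part of secondary outcome 7, one of ten secondary outcomes. A reader might extend the concern to body weight or to CDAI remission; nothing in the documents shows that either is affected. The change is still worth making before data collection, because supplement starts that were never recorded cannot be accounted for later.

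**What to change.** 1. Reconcile Intervention items 1 and 2 so that one supplement rule is stated for all three arms, for example beside the other all-arm dose rules. Its clinical content is for the sponsor's clinicians. A common rule may change what some patients are permitted to take, so it should be settled as a clinical decision and not treated as a purely editorial move.
2. Add a CRF line in all arms for every start or dose change of a vitamin, mineral or nutritional product, with product and date.
3. Report outcome 7 per analyte on all randomised patients, with supplement starts tabulated by arm. Do not use exclusion of patients who started a supplement as the check: it selects on low baseline levels after randomisation and can push the contrast in the same direction as the bias.

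The cost is one sentence, one CRF line and one table. Sample size, visits and assays are unchanged.

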Patients will be instructed to take the allocated treatment and to collect empty bottles/blisters of medication to assess the compliance at the next visit. Six weeks later (visit 3), their symptoms will be re-assessed, blood, urine and stool samples collected and SHAPE study performed. Patients will be instructed to stop the EEN or decrease the dose of CS, as detailed in the section “Follow up after treatment”. In the last visit (4th visit; 10 weeks after enrollment) we will collect information on symptoms, stool samples and urine.

The study protocol will be submitted by the investigator for approval by the Hamilton Integrated Research Ethics Board (HiREB).

Randomization process

The sequence of the treatments will be randomly generated using a computer-based pseudo-random number generator (RStudio Team (2015). RStudio: Integrated Development for R. RStudio, Inc., Boston, MA) Patients will receive one of challenges A,

B, or C consisting of CS, ECS or ECSC. A third person not involved in the study will perform the randomization to preserve treatment allocation concealed from participants and study staff. A block randomization will stratify patients by disease location (colonic/small bowel involvement). Each treatment will be assigned a number according to the randomization sequence. On recruitment, the patient will be assigned into one of three strata and given the next consecutive randomization number available for that stratum. Treatment will be not blinded for patients or study staff.

Subject recruitment

Subjects will be recruited from McMaster University Medical Centre (MUMC) Digestive Diseases Clinic, identified in an ongoing database organized in 2008 and by recruitment flyers posted at McMaster University Medical Centre, Juravinski Hospital and Hamilton General Hospital. Patients in the database signed an informed consent agreeing to be contacted for future research. Patients will be contacted by study personnel and invited to participate in the study.

After the subject has provided written consent to participate, an inclusion checklist will be completed. Subjects will be enrolled after having fulfilled all inclusion criteria, and none of the exclusion criteria.

Participants

One hundred adult patients diagnosed with IBD will be recruited at McMaster University Medical Centre. This will provide 30 subjects in each treatment arm, allowing for 10% dropout rate.

Inclusion criteria:

1. Adult patients (age 18-75 years)

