- Systemic priming to gut bacteria ([name] Lab using Flow cytometry after incubating patients' serum with cultured fecal bacteria¹⁶)
- First urine morning for metabolomics
- Intestinal permeability – indirect markers of mucosal integrity (FABP2)

Statistical analysis

There is no previous estimate on the effect of ECS compared to CS in inducing symptomatic improvement and associated changes in gut microbiota composition. Therefore, a sample size of 30 patients per arm^{28,29} should be sufficient to estimate the results and allow us to plan for future larger study. We will recruit additional 10 patients in total, to account for drop outs rates. Results will be analyzed as intention to treat (for primary outcome) and per protocol (excluding patients non-compliant with EN). The results will be expressed as n (%), mean (SD) or median (IQR) as appropriate. We will perform logistic regression to assess the association between symptomatic response and significant changes in gut microbiota composition in each group. T test or Man Whitney U test will be used as appropriate to assess differences between means. Analysis will be performed using SPSS version 21 (San Diego, CA).

Early withdrawals:

The following criteria will be considered as reasons for early discontinuation from the study (drop outs):

- Patient's decision.

- Physician's decision in case that the continuation of the patient in the study places him/her at risk.
- Patients that were not compliant with the unauthorized concomitant diets/treatments/medication will be considered as non-compliant and considered for the ITT analysis. If a subject's outcome measures worsen to the degree that they meet the study's Exclusion Criteria, study treatment will be withdrawn. Medical care will be provided as directed by the study physician and/or the subject's physician. If the required medical care conflicts with the study protocol, the subject will be placed in the intent-to-treat group. Study safety follow up will continue unless the subject withdraws, and/or is withdrawn by the study physician, and/or on the advice of the subject's physician.

Handling of adverse events

Reporting and documentation of adverse events

All adverse events occurring during the study will be reported and recorded whether or not they are considered to be non-serious, serious and/or related to the treatment. The following information will be required in each case:

- Subject and date
- Description of event
- Duration
- Frequency

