***Standard corticosteroids tapering regimen (ECS)**

Week	1	2	3	4	5	6	7	8	9	10
CS mg/day	40	40	35	30	25	20	15	10	5	5 mg every other day

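### The per-protocol rule selects on formula adherence only, so it cannot remove a CS patient for poor adherence, and no analysis population is named for the secondary outcomes

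*Combined protocol and SAP*

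**What the plan says.** The analysis sets are given in one sentence of Statistical analysis: "Results will be analyzed as intention to treat (for primary outcome) and per protocol (excluding patients non-compliant with EN". Secondary outcomes and endpoints lists ten outcomes, the tenth being adverse events, and assigns none of them to a population.

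The Intervention section shows who can be non-compliant with formula: "Patients randomized to ECS or ECSC arms will receive EEN defined as enteral feeds given exclusively as sole nutritional source". For the third arm it says: "Patients randomized to the CS arm will be asked to maintain their regular diet".

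Treatment compliance is wider than the per-protocol rule. It classes as non-compliant any patient "consuming <80% of the prescribed treatment dose throughout the study, or those who interrupted therapy for more than three consecutive days", without limiting this to formula, and asks patients to "keep the cans of Modulen and blister packs of prednisone during the entire treatment period". Study design separately tells them to "collect empty bottles/blisters of medication to assess the compliance at the next visit", and that visit falls six weeks later.

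Early withdrawals adds two statements that apply to any arm. Patients with unauthorised concomitant diets, treatments or medication count as non-compliant and are considered for ITT. Subjects whose necessary care conflicts with the protocol are assigned to the ITT group. Neither statement says that these patients leave the per-protocol set, and neither deals with low prednisone intake.

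**The concern.** A per-protocol comparison is always open to selection, because adherence is observed after randomisation and may be related to outcome. Here the selection is also lopsided. Formula non-compliers leave ECS and ECSC, while a CS patient who takes little prednisone stays in. An ECS or ECSC patient who takes the formula but not the prednisone stays in as well. The plan measures prednisone adherence and then does not use it to define the set.

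This matters because estimation is the purpose of the pilot. General aim and endpoint asks for effect sizes with intervals on every measure, to plan a powered trial. If the secondary estimates come from the stated per-protocol set, a selection effect present in the EEN arms and absent from CS is carried into that planning. If the population is simply undefined, it can be chosen after the data are seen, in a trial whose Randomization process section says treatment is not blinded.

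**Working it through.** **The plan's own figure.** Participants gives 100 recruited, 30 per arm and 10% dropout. Three arms of 30 make 90, and 90 / (1 − 0.10) = 100, as stated. The documents give no remission rates, power or non-compliance rate, so there is no further figure to reproduce.

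**Who the stated rule can exclude for adherence.**

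| Patient | Non-compliant under Treatment compliance? | Excluded by the stated per-protocol rule? |
|---|---|---|
| ECS/ECSC, low formula intake | Yes | Yes |
| ECS/ECSC, formula taken, low prednisone intake | Yes | No |
| CS, low prednisone intake | Yes | No |

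**Size, under assumptions.** None of the following is in the documents except the 30 per arm: no true treatment effect; 60% response in each arm; a fraction f of the EEN arm dropped as formula non-compliers; response g higher in compliers than in non-compliers; CS left at 30.

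Let a be the complier response. Then 0.60 = (1 − f)a + f(a − g), so a = 0.60 + fg. The spurious difference is therefore f × g.

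The 95% half-width is 1.96 × √(0.24/n + 0.24/30), where n = 30(1 − f) and 0.24 = 0.60 × 0.40.

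| f | n in EEN arm | g = 10 points | g = 20 | g = 30 | Half-width (points) |
|---|---|---|---|---|---|
| 10% | 27 | 1 | 2 | 3 | 25.5 |
| 20% | 24 | 2 | 4 | 6 | 26.3 |
| 30% | 21 | 3 | 6 | 9 | 27.3 |
| 40% | 18 | 4 | 8 | 12 | 28.6 |

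If non-compliers do better, every shift changes sign.

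**False-positive rate.** For a two-sided 5% test this is P(|Z + shift/SE| > 1.96), with SE = half-width/1.96:
- f = 10%, g = 10: 5.1%
- f = 20%, g = 20: 6.0%
- f = 40%, g = 30: 13.0%

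In the last case the modelled complier rate is 72%. Using its own variance (0.72 × 0.28 = 0.2016) gives a half-width of 27.2 points and a rate of 13.9%, so the simplification does not inflate the result.

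**Continuous outcomes.** With assumed gaps of 0.2–0.6 SD, the shift runs from 0.1 × 0.2 = 0.02 SD to 0.4 × 0.6 = 0.24 SD. At 24 versus 30 patients the half-width is 1.96 × √(1/24 + 1/30) = 0.54 SD.

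**What a symmetric rule leaves.** The residual is (f in EEN − f in CS) × g. With 20% and 10%, gaps of 10, 20 and 30 points leave 1, 2 and 3 points, instead of 2, 4 and 6.

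**The case against.** The best counter-argument concerns reach. A reader might infer that the plan commits the secondary outcomes to per protocol only. It does not say so. The limit placed on ITT makes that a natural reading, since it would have little function if ITT covered everything. But the Early withdrawals text mentions ITT without tying it to the primary outcome, which fits a general ITT population. If ITT is also run for the secondary outcomes, the asymmetry touches only a supplementary analysis. This objection stands: the firm defect is an unnamed population, and bias in the secondary estimates is conditional.

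A reader might also infer that nobody except formula non-compliers can leave the per-protocol set. That goes too far, because Early withdrawals could be taken to remove patients in any arm for unauthorised treatment or conflicting care. It still would not select CS patients on prednisone adherence.

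A third tempting inference is that the results are known to be tilted towards EEN. The documents give no outcome by compliance, so the direction is open, and the ITT primary comparison is not exposed to this selection.

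Finally, the shift is modest: in the middle case, 4 points against a half-width of about 26. That is fair, but the shift is systematic, and a trial run to produce estimates should not build it in.

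**Conclusion.** The concern holds in this form. The stated per-protocol rule is asymmetric: it selects EEN patients on formula adherence, cannot remove a CS patient for poor adherence, and disregards prednisone adherence in all arms. Confidence in this is high, because it follows from the text and nothing elsewhere overrides it. Any per-protocol ECS-versus-CS estimate, including the per-protocol version of the primary outcome, inherits the problem.

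Confidence that the secondary estimates are biased is medium. It depends on their being analysed per protocol only, and on formula non-compliers differing in outcome from compliers. On the assumed ranges the distortion is well inside sampling error for a single comparison, and of unknown sign. It should be fixed, but it does not undermine the ITT primary analysis.

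**What to change.** 1. State that ITT, meaning all randomised patients in their allocated arm, is the main analysis for every between-arm outcome. Report adverse events in all treated patients by allocated arm; their analysis set is currently unstated. How missing week-6 data are handled is a separate choice and is not set here.

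2. Keep per protocol as supportive only. Apply the existing Treatment compliance definition to each arm's full allocated treatment, formula and prednisone, counting treatment prescribed up to the week-6 visit. The cut-off is needed because that definition runs over the whole study. The standard prednisone schedule in Figure 1 lasts 10 weeks, 4 of them (40%) after that visit, whereas the short course, described as "for 3 days and taper in 16 days", is over well before it. Without a cut-off, weeks 7–10 could decide who enters a week-6 comparison in CS and ECS but not in ECSC.

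3. Reconcile Study design, where bottles and blisters are checked at the six-week visit, with Treatment compliance, where packs come back when the treatment period ends, so that a week-6 prednisone count exists.

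4. Replace the Early withdrawals wording on the ITT group with, for example: *Patients in any arm who use unauthorised diets, treatments or medication, or whose required care conflicts with the protocol, remain in the ITT analysis in their allocated arm and are excluded from the per-protocol analysis.*

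The cost is mainly wording. Compliance is already recorded in the CRF, and no new data are needed if packs are checked at six weeks as Study design says; if they are returned only when treatment ends, a week-6 prednisone count must be added. Estimates may become less favourable to EEN. A symmetric rule reduces the selection bias but need not remove it, since EEN patients have two components on which to fail and CS patients one. That is why ITT should lead.
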